6 STUDY CONDUCT AND DESCRIPTION OF STUDY PROCEDURES

6.1 Study Materials

The following study materials will be provided at the study start:

- Investigator File/Study Binder
- Drug Accountability Logs
- Sample source documents
- Concomitant and Rescue Medication Logs (take home for subject)
- Investigator Brochure
- Interactive Web-based Response System (IWRS) manual
- Electronic Case Report Forms (eCRF)
 - o Electronic Case Report Forms (eCRFs) will be prepared for all data collection fields
- eCOA Handheld devices
 - o One device to be kept onsite for training purposes with training materials
 - Supply of devices for each randomized subject to receive one device to use during the treatment phase
- Drug administration instructions
- Laboratory kits and laboratory manual
- Home pregnancy test for each randomized subject of WOCBP
- ECG Machine and instructions
- Serious Adverse Event (SAE) forms and Serious Adverse Events (SAE) Reporting instructions
- Pregnancy surveillance forms
- S-STS source documents

- Single use, disposable nasal speculum provided upon request
- Study system access:
 - Electronic Data Capture (EDC) tool to submit study data to Sponsor/ CRO
 - o IWRS
 - Central Laboratory

Safety laboratory, plasma, serum, instructions for all specimens collected will be provided by a designated central laboratory. ECG equipment, supplies, instructions and training materials will be supplied by a centralized ECG vendor.

6.2 Safety Assessments

6.2.1 Vital Signs and Physical Measurements (Height and Weight)

Body weight and height will be recorded at the scheduled visits as outlined in Table 1.

6.2.2 Electrocardiogram (ECG)

A standard 12-lead ECG will be recorded during the Screening Phase and at the scheduled visits as outlined in Table 1. A central ECG service will be utilized for all ECGs and the Investigator will determine if any abnormalities are clinically significant or not.

6.2.3 Physical Exam

Subjects will undergo a routine physical examination during the Screening Phase and at the scheduled visits as outlined in Table 1. Physical exam will include nasal inspection.

6.2.3.1 Nasal Inspection

The nasal passages and turbinates will be visually inspected by the Investigator or medically qualified delegate with a nasal speculum or otoscope at the screening, baseline and end of treatment visits to detect evidence of significant nasal conditions that may affect the administration or absorption of the nasal product (e.g. severe septum deviation, nasal deformity or blockage, inflammation, perforation, mucosal erosion or ulceration, polyposis, nasal trauma). Nasal findings will be recorded as appropriate and followed until resolution.

6.2.4 Laboratory Assessments

6.2.4.1 Safety Laboratory Testing

Blood and urine samples will be obtained as outlined in Table 1 for clinical laboratory evaluations. A central laboratory vendor will be utilized for this study and a laboratory manual will be provided to each site. If possible, subjects should be fasting for a minimum of 8 hours prior to all blood draws. However, if a subject is not fasting at a given visit, the blood draw should still be performed, and the non-fasting status should be documented.

Hematology: Hemoglobin, hematocrit, red blood cell count, white blood cell count (WBC) with differential, and platelets.

Blood chemistry/electrolyte: Sodium, potassium, chloride, bicarbonate, calcium; glucose, BUN (urea), serum creatinine, uric acid, ALT, AST, alkaline phosphatase, LDH, total protein, albumin, total bilirubin, direct bilirubin, indirect bilirubin, CK. End of Treatment Visit – elevations in CK (>5x ULN) may have further CK fractionation tests performed.

Lipid panel: Cholesterol, LDL, HDL, triglycerides (Screening Only).

Estimated glomerular filtration rate: eGFR using the estimated MDRD formula will be calculated and reported by the central lab at each visit that clinical laboratory tests are collected as outlined in Table 1.

Urinalysis: pH, specific gravity, ketones, nitrites, urobilinogen, leukocyte esterase, protein, glucose and blood. If blood, protein or leukocytes are positive, reflex to microscopic examination.

Urine Drug Screen: For drugs of abuse.

6.2.4.2 Pregnancy Testing

Pregnancy tests will be conducted (serum, urine, or home pregnancy test), when appropriate and as outlined in Table 1.

6.2.5 Sheehan Suicidality Tracking Scale (S-STS)

The S-STS is a prospective clinician administered rating scale that contains questions that track both treatment-emergent suicidal ideation and behaviors ^{17,18}. The S-STS will be completed on a paper form at the site. At the screening visit, the recall period for completing the S-STS is within the last 30 days prior to the screening visit; at all other visits, the recall period for completing the S-STS is since the last visit. Subjects who have a S-STS score of >0 should be evaluated by the Investigator. If the Investigator determines that a subject is at risk of suicide or self-harm,

appropriate measures to ensure the subject's safety and obtain mental health evaluation must be implemented. The subject must immediately be discontinued from the study. The event should be recorded as either an AE or SAE as determined by the Investigator and reported within 24-hours to the Sponsor.

6.3 Efficacy Assessments

6.3.1 Pain

Subjects are given an eCOA Handheld device to record their migraine pain score, on a 4-point numeric rating [no pain, mild pain, moderate pain, severe pain] at the time points indicated in Table 1.

6.3.2 Nausea, Phonophobia and Photophobia

The migraine associated symptoms of photophobia, phonophobia and nausea are measured on a two point scale (present or absent), using the handheld, at the time points listed in Table 1. If a subject reports the presence of a symptom, the subject is then asked to rate the severity of the symptom on a four point scale (none, mild, moderate or serve). All assessments are done using the handheld.

The subjects are also asked to identify their most bothersome symptom on the handheld (nausea, phonophobia or photophobia) at the onset of the migraine to be treated. The most bothersome symptom must be identified before the subject takes study medication.

6.3.3 Rescue Medication

The subject's use of rescue medication is recorded by the subject in a paper diary.

6.3.4 Functional Disability

Impact of treatment on functional disability will be assessed using a single-question scale. Subjects rate the level of disability they perceive as a result of their migraine in performing normal actions. This is done in the handheld, at the times indicated in Table 1, using a 4 point numeric rating scale (normal function, mild impairment, severe impairment, required bedrest).

6.3.5 Migraine Quality of Life Questionnaire

Impact of treatment on subject-reported quality of life will be assessed using The Migraine Quality of Life Questionnaire (MQoL) version 3.0. The MQoL is a 15-item instrument that has been validated in migraine subjects to assess the effect of migraine and its treatment on patients' health related quality of life in the following five migraine-specific domains: work functioning, social functioning, energy/vitality, feelings and concerns, and migraine headache symptoms. The handheld is used to evaluate the Migraine Quality of Life Questionnaire at 24 hours post-dose (see Table 1).

6.3.6 Migraine Preference of Medicine

The Preference of Medication Scale (PoMs) is a brief scale that captures the subjects' perception of whether the medication they are taking has had a greater benefit compared with previous medications to treat their pain. The handheld is used to evaluate the Preference of Medication Scale at 24 hours post-dose (see Table 1).

6.4 Early Discontinuation from the Study

Subjects MUST discontinue investigational product (and non-investigational product at the discretion of the Investigator) for any of the following reasons:

- Withdrawal of informed consent (subject's decision to withdraw for any reason)
- Any clinical adverse event (AE), laboratory abnormality or intercurrent illness which, in the opinion of the Investigator or sponsor, indicates that continued participation in the study is not in the best interest of the subject
- Pregnancy
- Termination of the study by Biohaven Pharmaceuticals, Inc.
- Loss of ability to freely provide consent through imprisonment or involuntary incarceration for treatment of either a psychiatric or physical (e.g., infectious disease) illness

All subjects who discontinue should comply with protocol specified End of Treatment procedures as outlined in Table 1. The only exception to this requirement is when a subject withdraws consent for all study procedures or loses the ability to consent freely (i.e., is imprisoned or involuntarily incarcerated for the treatment of either a psychiatric or physical illness).

7 STUDY DRUG MANAGEMENT

7.1 Description of Study Drug

7.1.1 Investigational Product

An investigational product, also known as investigational medicinal product in some regions, is defined as follows:

A pharmaceutical form of an active substance or placebo being tested or used as a reference in a clinical study, including products already with a marketing authorization but used or assembled (formulated or packaged) in a way different from the authorized form, or used for an unauthorized indication, or when used to gain further information about the authorized form.

The investigational product should be stored in a secure area according to local regulations. It is the responsibility of the Investigator to ensure that investigational product is only dispensed to study subjects. The investigational product must be dispensed only from official study sites by authorized personnel according to local regulations.

The BHV-3500 or the matching placebo will be provided in single use Aptar UDS devices fully prepared and ready for administration. The BHV-3500 and placebo solution are identical in appearance.

7.1.2 Non-investigational Product

Other medications used as support or rescue medication for preventative, diagnostic, or therapeutic reasons, as components of the standard of care for a given diagnosis, may be considered as non-investigational products.

In this protocol, non-investigational product(s) is/are: Not applicable for this study.

7.1.3 Packaging, Shipment and Storage

The product storage manager should ensure that the study medication is stored in accordance with the environmental conditions (temperature, light, and humidity) as determined by the sponsor. If concerns regarding the quality or appearance of the study drug arise, do not dispense the study drug and contact the sponsor immediately. Refer to the current Investigator Brochure for study medication storage requirements.

7.2 Dose and Administration

7.2.1 Method of Assigning Subject Identification

At the time of enrollment, immediately after written informed consent is obtained and before performing any study-related procedures, each subject will be assigned an unique sequential 4-digit subject number beginning with 0001, 0002, 0003, etc. for identification throughout the

study through the IWRS. This subject number must not be reused for any other subject in the study. The physician/coordinator must contact the IWRS to enroll each subject into a centralized database at the time of signing consent.

After completion of all screening evaluations all eligible subjects will be randomized in a 3:1 ratio to the BHV-3500 or placebo treatment groups. The randomization will be stratified by the use of prophylactic migraine medications (yes or no). It is important to correctly enter subjects who are using prophylactic migraine medication in the IWRS system. Once a patient is stratified in the IWRS, this cannot be changed and will be considered a significant deviation.

Randomization schedules will be generated and kept by the IWRS vendor in a secure network folder with access limited to only unblinded team members. Each subject who is qualified for treatment will be randomized via the IWRS randomization option. Subjects will maintain their subject number assigned at screening throughout the trial. The IWRS will provide the double-blind treatment assignments.

The randomization will trigger a kit number for the randomized treatment type. The drug will be dispensed at the time of randomization.

7.2.2 Selection and Timing of Dose and Administration

Study medication (Aptar UDS containing BHV-3500 or matching placebo) will be packaged in a carton. There are no dose adjustments in this study and subjects will receive study medication sufficient to treat one migraine headache of moderate or severe intensity within 45 days of randomization (Baseline Visit). Subjects will be dispensed the study medication at randomization (Baseline Visit) and will take the Aptar UDS from the carton at the time of moderate or severe migraine headache onset *ONLY after answering questions regarding their migraine symptoms in the handheld* device. Subjects will administer a single spray of the medication from the device. Subjects must inform the study staff if they sneeze, if the device malfunctions or if the device does not dispense a complete spray.

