4 STUDY PLAN

4.1 Study Design and Duration

This is a double-blind, randomized, multicenter, outpatient evaluation of the safety and efficacy of BHV-3500 as compared to placebo in the treatment of moderate or severe migraine. Subjects will be dispensed one Aptar Unit Dose System (UDS) liquid spray device containing a single dose of study medication BHV-3500 or a matching placebo. The total duration of the study will be approximately 11 weeks. This includes a 3-28 day Screening Period, a Treatment Phase that can last up to 45 days or until the subject has a migraine that reaches moderate or severe intensity, followed by an End of Treatment Visit 7 (+2) days after the administration of study medication.

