4.3.2 Randomization Phase (45 days)

Subjects will return to the study site for the Baseline (Randomization) Visit.

Subjects who meet all eligibility criteria they may be randomized at the Baseline Visit. Randomization will occur in the IWRS. The subjects will be provided with an eCOA Handheld device. The study personnel will instruct the subject on the proper use of the handheld to ensure proper understanding and use of the tool, prior to the subject leaving the office.

After randomization is completed in the IWRS, study medication will be dispensed to subjects to take home for up to 45 days. The study personnel must train the subject on the proper use of Aptar UDS device using instructions to be provided to each study subject. This study medication is to be taken when a migraine attack reaches moderate or severe intensity on the numeric rating scale (NRS) as indicated in the handheld. The subject will be instructed to take their study medication, as an outpatient, when (if) they have a migraine headache which reaches moderate or severe intensity after they have answered questions about their current pain and symptoms and identified their currently most bothersome, migraine associated, symptom (phonophobia, photophobia or nausea) in the handheld. The subject will complete assessments for forty-eight hours after taking study medication to record efficacy and other quality of life measures.

Subjects in this study may be randomized only once. Under no circumstances may a subject be re-randomized.

4.3.2.1 eCOA Handheld Device Data Collection

The eCOA handheld device may also be referred to as a handheld or an eDiary. Once a subject experiences a headache of moderate to severe intensity, they should record this in the handheld. The handheld will instruct the subject to take study medication after the initial assessments are completed in the device.

The following will be recorded in the eCOA handheld device:

- Onset time of headache, intensity of the headache prior to and at time of taking study medication
- Headache severity will be recorded using a four-point numeric rating scale (no pain, mild pain, moderate pain, severe pain) at the onset of the migraine and after dosing at time points of 15, 30, 45, 60, and 90 minutes and 2, 3, 4, 6, 8, 24 and 48 hours

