### 6.2.5 Exposure

#### 6.2.5.1 Study Medication

Subjects report study drug exposure in the eDiary, whereas sites report study drug accountability on the Study Drug Accountability CRF.

eDiary study drug exposure will be summarized by as-randomized treatment group, All BHV-3500, and overall for randomized subjects, and will include the number and percentage of subjects in the following categories:

- Study drug taken (i.e., study drug start date/time not missing)
  - o Study drug taken mistakenly before using eDiary (see Section 7.6.3.1)
  - Study drug actually received different from randomized treatment assignment (i.e., astreated treatment group not equal to as-randomized treatment group).

• Study drug not taken (i.e., study drug start date/time missing).

Study drug accountability will be summarized by as-randomized treatment group, All BHV-3500, and overall for randomized subjects, and will include the number and percentage of subjects in the following categories:

- Kit dispensed and returned
  - Investigational product (IP) used
  - o IP not used
  - o IP use unknown or not reported (i.e., missing)
- Kit dispensed and not returned.

Two 2 x 2 cross-tabulations of eDiary study drug exposure and study drug accountability will be provided for randomized subjects by overall only. The number and percentage of subjects in each category will be summarized follows:

- Categories for study drug exposure in rows are "study drug taken" and "study drug not taken". Categories for study drug accountability in columns are "kit dispensed and returned" and "kit dispensed and not returned".
- Categories for study drug exposure in rows are "study drug taken" and "study drug not taken". Categories for study drug accountability in columns are "IP used" and "IP not used/unknown/not reported".

A by-subject listing of eDiary study drug exposure and study drug accountability will be provided for randomized subjects. Subjects for whom the eDiary study drug exposure and study drug accountability categories (as per cross-tabulations) do not match will be flagged.

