# 6.5.6 Nasal Inspection

Nasal inspections will evaluate evidence of edema and inflammation in the left and right nostrils with yes or no responses. Abnormalities are considered to be "yes" responses.

A by-subject listing of nasal inspection will be provided for enrolled subjects.

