# 6.5.6.1 Nasal Inspection Abnormalities

On-treatment nasal inspection abnormalities will be summarized for each parameter as the number and percentage of subjects with abnormalities for the following parameters: nasal edema or nasal inflammation in either nostril; nasal edema in left nostril; nasal edema in right nostril; nasal inflammation in left nostril; nasal inflammation in right nostril. Percentages will be based on subjects with non-missing data for each parameter.

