## 6.5.6.2 Nasal Inspection Evidence Shift from Baseline

Nasal inspection evidence shifts from baseline to an on-treatment abnormality will be summarized for each parameter (nasal edema in left nostril; nasal edema in right nostril; nasal inflammation in left nostril; nasal inflammation in right nostril) as the number and percentage of subjects in each evidence category (yes or no).

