# 7.6.3 eDiary Data

# 7.6.3.1 Study Medication

### eDiary Migraine Report

If the subject answered "yes" to taking study medication mistakenly already before using the eDiary, then the eDiary Migraine Report will collect study medication time if the subject reported taking it today or yesterday; otherwise, only the study medication date will be collected.

Otherwise, if the subject answered "no" to taking study medication mistakenly already, had a current pain level of moderate or severe, and answered "yes" to confirming having taken study medication, then the eDiary Migraine Report will record the time the subject has confirmed taking study medication (i.e., finding date/time) as the study medication time.

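### The plan does not describe recording which nostril was dosed, so its left/right nasal rows, including the whole shift table, cannot separate exposed from unexposed nostrils

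*Protocol*

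**What the plan says.** **Exposure.** Protocol 4.1 says "Subjects will be dispensed one Aptar Unit Dose System (UDS) liquid spray device containing a single dose of study medication", and 7.2.2 adds "Subjects will administer a single spray of the medication from the device". One spray means one nostril, although neither document says so or names a side. Protocol 4.3.2 refers to separate instructions: "The study personnel must train the subject on the proper use of Aptar UDS device using instructions to be provided to each study subject". Those instructions are not part of the protocol or SAP.

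**What is recorded about the dose.** SAP 6.2.5.1 says "Subjects report study drug exposure in the eDiary, whereas sites report study drug accountability on the Study Drug Accountability CRF"; its categories cover drug taken or not, kit returned or not, and product used or not. SAP 7.6.3.1 says that, for a subject who doses as intended, "the eDiary Migraine Report will record the time the subject has confirmed taking study medication". The site-completed Study Medication Intake Report holds a date and time. The handheld list in Protocol 4.3.2.1 and the derived dates in SAP 7.3 add nothing about side.

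**Outcome.** SAP 6.5.6 says "Nasal inspections will evaluate evidence of edema and inflammation in the left and right nostrils with yes or no responses". The abnormality table in 6.5.6.1 has five parameters, one composite and four by side, beginning "nasal edema or nasal inflammation in either nostril; nasal edema in left nostril; nasal edema in right nostril". The shift table in 6.5.6.2 has only the four by side, beginning "nasal edema in left nostril; nasal edema in right nostril". Inspections take place at screening, baseline and end of treatment.

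**The concern.** The local outcome is held by nostril but the exposure is not. For a one-spray product, left and right mean little in themselves; the informative split is dosed against undosed. Without the side, a left or right row averages exposed and unexposed nostrils in unknown proportion, which shrinks any difference between active and placebo.

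Local tolerability by dose is a natural safety question for an intranasal dose-ranging trial that aims to find a safe, well-tolerated dose. The shift table is the only planned nasal table that accounts for findings already present at baseline, and every row in it is by side. The undosed nostril, which could serve as a within-subject reference, goes unused.

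**Working it through.** The documents give no nasal finding rate, effect or power, so there is no stated figure to reproduce. The rates below are assumptions.

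**Inputs**
- One spray per subject (Protocol 7.2.2).
- About 380 subjects per arm (SAP 5), used for illustration only.
- q, the share of subjects dosing the left nostril: not given; taken as 0.5 to 0.9.
- b, the background rate per nostril of the finding tabulated: not given; taken as 0.5% to 10%.
- d, the drug excess in a dosed nostril: not given; taken as 2 or 5 percentage points.

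**Step 1: side-specific rows.** The active-minus-placebo difference is q × d in the left row and (1 − q) × d in the right row. With d = 5 points:
- q = 0.5: 2.5 and 2.5 points (50% and 50% of the effect)
- q = 0.7: 3.5 and 1.5 points (70% and 30%)
- q = 0.9: 4.5 and 0.5 points (90% and 10%)

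If the instructions fix one side (q = 1 or 0), one row shows all of d and the other none, but the SAP does not say which row is which.

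**Step 2: either-nostril row.** With independent nostrils, the active rate is 1 − (1 − b)(1 − b − d) and the placebo rate is 1 − (1 − b)². The difference is d(1 − b), whatever q is. With d = 5 points:
- b = 0.5%: 4.98 points (99.5% kept)
- b = 2%: 8.86% − 3.96% = 4.90 points (98%)
- b = 5%: 4.75 points (95%)
- b = 10%: 23.5% − 19.0% = 4.50 points (90%)

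If background findings are always bilateral, the row keeps all of d. In 6.5.6.1 this row is a composite, so b and d there refer to edema or inflammation together.

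**Step 3: how visible a difference would be.** No nasal test is planned, so this only ranks the rows. Two-proportion power, 380 per arm, two-sided 0.05, q = 0.5, independent nostrils:

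| b | d | dosed-nostril row | either-nostril row | left or right row |
|---|---|---|---|---|
| 0.5% | 5 points | 98% | 96% | 75% |
| 2% | 5 points | 92% | 79% | 49% |
| 10% | 5 points | 55% | 33% | 19% |
| 2% | 2 points | 37% | 24% | 14% |

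At b = 2%, d = 5 points and q = 0.7, the left row gives 72% and the right row 24%. The either-nostril row loses ground to the dosed-nostril row mainly because it carries the undosed side's background. With fully bilateral background the two rows coincide.

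**The case against.** The strongest reply is that the abnormality table already opens with an either-nostril row, which catches the dosed side whichever it was. That stands. A reader might infer from the left/right layout that every nasal row halves a local effect; the documents do not support this. The either-nostril row is barely diluted, and halving elsewhere needs an even split of sides that neither document gives.

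A reader might also infer that the side is never captured. The documents are silent, which is weaker: the case report forms, handheld screens and administration instructions were not available, and the instructions may fix a side.

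Further points on that side:
- The left and right excesses sum to d for any q, so a reader who adds them recovers the effect. That is true on average, but the SAP plans no such sum.
- An either-nostril shift can be derived from data already collected. This stands, and it supplies the cheapest part of the fix.
- The tables are descriptive and local events also reach the adverse event tables. Protocol 5.3 further limits background by excluding significant nasal conditions and nasal spray use. All of this limits the weight of the point.
- End of treatment is about a week after dosing, so transient findings may have gone. This also limits what the tables can show, but it is no reason to dilute what remains.

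**Conclusion.** The point holds in a limited form. The documents describe one exposed nostril, no item recording which, and a shift table made up only of left/right rows. Unless the administration instructions fix a side, those rows dilute a local effect to q and 1 − q of its size, and by half only at q = 0.5. If a side is fixed, the gap is that the SAP does not name it.

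The either-nostril row in 6.5.6.1 keeps about 90-100% of the effect for b up to 10%. It remains less sharp than a dosed-nostril row because it pools edema with inflammation and, unless background is bilateral, adds undosed-nostril findings. It has no counterpart in 6.5.6.2.

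The values of b, d and q are assumed, and the power figures illustrate summaries that carry no planned test. This is an inexpensive improvement to local-tolerability reporting; no efficacy conclusion depends on it.

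**What to change.** 1. **SAP 6.5.6.2, no new data.** Add either-nostril shift rows, one for edema and one for inflammation. Their limit should be footnoted: a new finding on the dosed side does not appear as a shift when the other side already had one at baseline.
2. **One data item.** Add nostril used (left, right, unknown) to the dose confirmation in the eDiary Migraine Report and to the Study Medication Intake Report. If the device instructions fix a side, state it in the SAP instead.
3. **SAP 6.5.6.1 and 6.5.6.2.** Present dosed-nostril and undosed-nostril rows for edema and inflammation, with side unknown shown separately. Keep the either-nostril row, and read the undosed nostril as the within-subject reference.

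Step 1 costs a SAP edit and some programming. Steps 2 and 3 cost one handheld and form item plus relabelled rows. Subjects who have already dosed could be asked at End of Treatment, but some sides will then be recalled about a week later or remain unknown.
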